155 orals agents [40, 41, 43-48]. It is still not known whether these favorable effects extent to  
156 the more challenging group of patients with type 2 diabetes who have a baseline HbA1c  
157 >10%. Liraglutide reduces blood glucose by several mechanisms independent of insulin  
158 secretion and its superior effect on HbA1c and weight loss was found to be largely  
159 independent of diabetes duration and baseline HbA1c [39]. Treatment with GLP-1  
160 agonists has also been associated with low secondary failure rates, durable and sustained  
161 long term blood glucose control, and durability of the initial weight loss [39, 42, 49].

162

163 **Given all these distinct properties of GLP-1 agonists and simplicity of use, we**  
164 **propose they could represent a viable alternative to intensive insulinization in**  
165 **patients with very uncontrolled (HbA1c >10%) type 2 diabetes.**

166

167 The aim of this study is to compare a GLP-1 plus basal insulin treatment regimen to a  
168 basal-bolus treatment regimen in patients with very uncontrolled (HbA1c>10%) type 2  
169 diabetes. We will compare the two regimens with respect to efficacy in improving  
170 glycemic control, rate of hypoglycemia, change in weight, effect on patient quality of  
171 life, treatment burden, physician time, as well as healthcare related cost. We hypothesize  
172 that the two treatment regimens will have equal effectiveness, while the GLP-1 based  
173 regimen will be superior with respect to all other variables.

174

175 We chose to focus on a specific patient population which is generally considered to be  
176 most challenging to manage, use up greater healthcare resources, have higher potential for  
177 morbidity, and have traditionally been excluded from most clinical trials. Therefore this  
178 study will fill in an existing knowledge gap and provide high level evidence for future  
179 diabetes treatment guidelines pertaining to this patient population. We will obtain  
180 information not only in regards to the effectiveness of the treatment, but also safety and  
181 impact on healthcare cost beyond the cost of the drug.

182

183 Our findings will have great impact on the way we treat this – unfortunately – significant  
184 segment of the diabetic population, with huge potential benefits beyond just glycemic  
185 control, including quality of life, other metabolic co-morbidities, healthcare cost, etc.  

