**STATISTICAL CONSIDERATIONS:**

**Sample Size Calculation**

We propose to test a non-inferiority hypothesis comparing the 6-month change from baseline in HbA1c between the two treatment groups, with a non-inferiority margin of 0.4%. We conservatively estimate the standard deviation of the difference at 0.5% based on results from reported studies with similar design[44, 45, 47]. Using a one-sided alpha of 0.025, we determine that 44 subjects per group completing 6 months will provide power 0.96 to test this non-inferiority hypothesis, shown below amongst with other scenarios (Hintze, J. (2011). PASS 11. NCSS, LLC. Kaysville, Utah, USA. [www.ncss.com](http://www.ncss.com)). We will need to randomize 100 patients to test this hypothesis assuming a 12% drop-out rate (estimated drop-out rate based on our extensive prior experience with similar population and length of study). We plan to screen 120 patients to account for approximately 20% anticipated screen failures.

Power and sample size estimation for Non-Inferiority Test (H0: Diff >= NIM;  
H1: Diff < NIM)  
Higher Means are Worse  
Test Statistic: T-Test

Power	N1/N2	Non-Inferiority Margin (NIM)	Actual Difference (D)	Significance Level (Alpha)	Beta	Standard Deviation1 (SD1)
1.000	44/44	0.4	0	0.025	0.000	0.3
1.000	48/48	0.4	0	0.025	0.000	0.3
1.000	50/50	0.4	0	0.025	0.000	0.3
0.960	44/44	0.4	0	0.025	0.040	0.5
0.973	48/48	0.4	0	0.025	0.028	0.5
0.977	50/50	0.4	0	0.025	0.023	0.5
0.755	44/44	0.4	0	0.025	0.245	0.7
0.791	48/48	0.4	0	0.025	0.209	0.7
0.808	50/50	0.4	0	0.025	0.192	0.7

Further, this sample size will yield at least 80% power at two-sided alpha=0.05, superiority hypothesis, for the secondary composite outcome endpoint of HbA1c<7% with no hypoglycemia and no significant weight gain, expecting that 25% and 5% reach

726 this endpoint with liraglutide treatment and standard basal-bolus insulin treatment,  
727 respectively.

728

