### 735 **Statistical Analysis Plan**

736 All statistical analyses will be performed by the study statistician ([name]), who  
737 has extensive experience in clinical trials analysis.

738 Primary analysis: The primary analysis will be intention-to-treat (ITT) which will include  
739 all randomized participants who receive at least one dose of a study medication. The  
740 non-inferiority of liraglutide treatment strategy compared to standard basal-bolus insulin  
741 regimen will be assessed using a 95% confidence interval for the between treatment  
742 group net difference (month 6 minus month 0) in HbA1c at 6 months. This 95%  
743 confidence interval will be derived from the differences of least square means estimated  
744 from a mixed model repeated measures analysis. Non-inferiority of liraglutide treatment  
745 will be concluded if the upper limit of the 95% confidence interval is less than the non-  
746 inferiority margin of 0.4%.

747

748 Secondary analyses: We will also perform a per-protocol analysis comparing HbA1c  
749 response because, in non-inferiority hypothesis testing, the ITT analysis may be biased  
750 toward the null hypothesis. The per-protocol population is defined as the population who  
751 continued the assigned intervention as randomized for the duration of the study period.  
752 Secondary outcomes include the composite endpoint of HbA1c<7% with no  
753 hypoglycemia and no significant weight gain, a binary variable, which will be compared  
754 between the randomized study groups with a logistic regression model. The odds ratio  
755 and corresponding 95% confidence intervals will be reported. From healthcare related  
756 cost data, cost-effectiveness ratios will be summarized as point estimates with 95%  
757 confidence intervals, accounting for the skewness in the distribution of the ratio[50].  
758 Sensitivity cost analyses will be performed to further assess variables such as treatment  
759 failure and quality of life weights. Multiple logistic regression models will be constructed  
760 to evaluate any association of baseline covariates on treatment efficacy. Binary  
761 secondary endpoints will also be assessed with logistic regression models. Group  
762 comparisons and changes from baseline over time (study visits) of continuous secondary  
763 outcome variables will be analysed with mixed model repeated analysis. The logrank test  

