764 will be used to compare the pre-specified “treatment failure” end-point between groups.  
765 Safety endpoints and hypoglycemic and other adverse events will summarize in detail  
766 with descriptive statistics. The analysis of safety data will be performed for the ITT  
767 population.

768 Model assumptions regarding normality and covariance structure will be carefully  
769 assessed. Nonparametric tests or data transformations will be used if necessary to meet  
770 assumptions. Statistical analysis will be performed with SAS software (SAS Institute,  
771 Cary NC), particularly Proc Mixed for linear models with both fixed and random effects.

772 A two-sided alpha <5% will be considered significant for all analyses.

773

774 **Interim Analysis**

775 No interim analysis is planned.

776

777 **DATA HANDLING AND RECORD KEEPING:**

778 All data will be collected in strict compliance with the University's HIPPA rules.

779 Research records (source documents) will be kept in a double-locked filing system in a  
780 secure locked room. Collected data will be stored in an electronic study database will be  
781 encrypted and password protected and saved on the University's secure network. Only  
782 study personnel will have access to these records.

783

784 The institutional review board (IRB) governing this study may inspect the medical  
785 records of any patient involved in this study at any time.

786

787 Laboratory specimens will be collected under standard of care protocol at Parkland  
788 hospital laboratory and handled in accordance with the hospital policy.

789

790 The study blind will be maintained by the designated statistician and only broken by  
791 request from a treating physician in case of a medical emergency.

792

793 **ETHICS:**

794 Ethical Considerations:

795 1. Exclusion of non-English speakers- while translators are available during working  
796 hours, the investigators are worried that no translator will be available to assure  
797 safety measures at all times.

798 2. Compliance with Insulin Regimen- At times patients are not compliant with  
799 complicated insulin regimens and providers often continue to uptitrate insulin  
800 dosage when patients remain above HbA1c goal. If patient compliance improves  
801 once enrolled in the study, there is a higher risk of hypoglycemia. Every effort  
802 will be made at all visits to determine exactly what amount of insulin the patient  

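### The cost-effectiveness ratio has no stated effect measure, ratio type or near-zero rule, and the versions that compare the arms are hard to interpret under the plan's own expectations

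*Combined protocol and SAP*

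**What the plan says.** The secondary analyses in the Statistical Analysis Plan state that "cost data, cost-effectiveness ratios will be summarized as point estimates with 95" per cent confidence intervals, with allowance for skewness of the ratio and a citation to a methods paper. Sensitivity cost analyses are to look at treatment failure and quality of life weights. The text does not name the effect measure, the ratio type or the interval method, and gives no rule for an effect difference close to zero.

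The closing aim statement of Background and Significance hypothesises "that the two treatment regimens will have equal effectiveness, while the GLP-1 based" "regimen will be superior with respect to all other variables". Healthcare cost is among the variables listed for comparison there. Under Sample Size Calculation the trial is planned "with a non-inferiority margin of 0.4" (per cent HbA1c), and every row of the power table sets the true difference to 0. The composite endpoint is expected in 25% of the liraglutide arm and 5% of the basal-bolus arm.

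Total and diabetes-related cost are also secondary outcomes in their own right (items 13 and 14). Continuous secondary outcomes go to a mixed model. On model assumptions, the same plan adds: "assessed. Nonparametric tests or data transformations will be used if necessary to meet" assumptions.

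**The concern.** An incremental cost-effectiveness ratio divides the cost difference by the effect difference. When the true effect difference is zero, the ratio has no stable value: its sign changes by chance, and its 95% interval may have no finite limits. Allowing for skewness does not help, because the difficulty is the position of the denominator and not the shape of the distribution. Sign is a separate difficulty. A negative ratio can mean cheaper and better or dearer and worse, and its size does not rank value in either case.

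At stake is whether the one analysis written specifically for cost gives a usable result. Leaving the denominator and method open also lets them be chosen after the data are seen. The primary HbA1c conclusion is not affected.

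**Working it through.** **Inputs.** Sample Size Calculation gives SD 0.5 (alternatives 0.3 and 0.7), 44 completers per group, 100 randomised, margin 0.4, one-sided alpha 0.025, true difference D = 0, and composite rates of 25% and 5%. The documents contain no cost figures, and none are used here.

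**Reproducing the plan's figure.** The standard error of the difference is 0.5 × √(2/44) = 0.1066, and the t critical value on 86 degrees of freedom is 1.988. The noncentral-t power at 0.4/0.1066 = 3.75 is 0.960, as stated. So 0.5 is being used as the per-group SD.

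**When an incremental ratio has a bounded interval.** Let ΔC and ΔE be the cost and effect differences, with variances V_C and V_E and covariance V_CE. The Fieller 95% set is all R with (ΔC − R·ΔE)² ≤ t²(V_C − 2R·V_CE + R²·V_E). The coefficient of R² is ΔE² − t²·V_E. The set is bounded only if this is positive, that is, only if the 95% interval for ΔE excludes 0. The probability of an unbounded set is therefore 1 minus the two-sided power on the denominator, whatever the costs are.

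**Denominator = HbA1c difference, 44 per group.** At D = 0 the probability is 0.95 by definition, at any SD or sample size (20,000 simulated trials: 0.95). Otherwise:

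| True difference D | SD 0.5 | SD 0.7 |
|---|---|---|
| 0.1 | 0.85 | 0.90 |
| 0.2 | 0.54 | 0.74 |
| 0.3 | 0.21 | 0.49 |
| 0.4 | 0.04 | 0.25 |

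For example, D = 0.1 with SD 0.5 gives noncentrality 0.1/0.1066 = 0.94 and probability 0.847.

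**Among trials that conclude non-inferiority.** At D = 0, non-inferiority is concluded in 0.960 of trials. The 0.025 whose interval lies wholly below 0 all count as successes, so the share of successes whose interval includes 0 is at most (0.960 − 0.025)/0.960 = 0.974. Simulation gives 97%; at D = 0.1 it gives 98%.

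**Denominator = composite, 25% versus 5%.** At 44 per group the standard error is √(0.25×0.75/44 + 0.05×0.95/44) = 0.073, so 0.20 is 2.7 standard errors from zero. Exact enumeration gives an effect interval that includes 0 in 0.196 of trials. At 50 per group it is 0.144 with a normal critical value and 0.164 with a t critical value. That is about 15 to 20%.

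**Sign on the composite.** The plan expects ΔE > 0 and ΔC < 0 for the liraglutide arm, so ΔC/ΔE < 0. The opposite result, ΔE < 0 and ΔC > 0, also gives ΔC/ΔE < 0.

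**Per-arm ratios.** Assume a mean HbA1c reduction of 1.9 to 3 points and an SD of 0.5 to 2. The denominator then lies between 1.9/(2/√44) = 6.3 and 3/(0.5/√44) = 39.8 standard errors from zero, which is stable. On the composite, the basal-bolus arm would be less secure: 0.05/√(0.05×0.95/44) = 1.5 standard errors, with a 0.95⁴⁴ = 10% chance of no responders. Neither version estimates a difference between the regimens.

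**The case against.** The plan does not say that the HbA1c difference is the denominator, or that the ratio is incremental. The composite is the main secondary outcome, is powered for superiority, and is the subject of the sentences just before the one on cost. The quality of life weights, although mentioned only for sensitivity analyses, leave room for a quality-weighted effect, for which the documents give no figures. This stands. A reader might infer that the interval will be unbounded in most trials, or for any HbA1c-based effect. The documents do not support that: the composite is HbA1c-based, and its interval would be bounded in about 80 to 85% of trials.

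Unboundedness is a property of the Fieller method, and the plan names no method. A percentile bootstrap would return finite limits. That is true, but with a denominator that straddles zero those limits mix ratios of opposite sign and cannot be read as a range of values.

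The plan also compares cost directly. Cost is a listed continuous outcome, and the default mixed model compares means. It would therefore be wrong to say that the plan has no comparison of mean cost. What remains is the fallback. Cost data are usually skewed, so a transformation or a nonparametric test is likely, and neither estimates the difference in arithmetic mean cost.

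Finally, one might infer that the cost aim, or a planned paper, depends on the ratio. Aim 4 asks for a comparison of costs and physician time and mentions no ratio. The Publication Plan says only that one paper may cover utilisation and cost.

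**Conclusion.** The concern holds as a gap in specification with a substantive consequence. The plan commits to a ratio without fixing its denominator, type, interval method or near-zero rule, and each plausible reading has a problem:

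- **Incremental on HbA1c change:** the Fieller set is unbounded in 95% of trials at the planned D = 0, and in 97% of those that conclude non-inferiority. It is unbounded in about 85% at D = 0.1. These figures assume a per-group SD of 0.5 and 44 per group, except that the 95% holds at any SD or sample size.
- **Incremental on the composite:** unbounded in only about 15 to 20% of trials at the expected 25% versus 5%, but the expected cheaper-and-better result is a negative ratio that cannot be ranked.
- **Per arm:** stable on HbA1c reduction under the assumed reductions and SDs, but not a comparison of the arms.

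For a quality-weighted effect the documents give nothing to calculate from. The point concerns a secondary analysis only. It is worth correcting before the data are analysed, because a better method is available on the same data.

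**What to change.** In the cost paragraph of the Statistical Analysis Plan:

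1. Name the effect measure used for cost-effectiveness.
2. Report the between-arm difference in arithmetic mean total cost and mean diabetes-related cost, each with a bootstrap 95% confidence interval. Exempt both from the general fallback to transformations or nonparametric tests.
3. Report incremental net benefit, λ·ΔE − ΔC, with a 95% confidence interval over a stated range of willingness-to-pay values λ, and show the joint bootstrap of ΔC and ΔE on the cost-effect plane. Net benefit is linear in both differences, so it stays defined when ΔE is zero and keeps cheaper-and-better apart from dearer-and-worse.
4. Quote an incremental ratio only when the effect interval excludes 0 and the result is a trade-off (dearer and better, or cheaper and worse).

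No new data are needed. The cost is SAP wording, a little more programming, and the need to state and defend a willingness-to-pay range for the chosen effect unit.

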## 211 **Specific aims:**

- 212 1. Compare the two treatment regimens with respect to a disease and patient-  
213 relevant composite outcome of effectiveness (HbA1c <7%) and safety (no  
214 hypoglycemia and no weight gain);
- 215 2. Compare the two treatment regimens with respect to treatment burden (number of  
216 daily shots, amount of glucose self-monitoring, need for treatment titration);
- 217 3. Compare the two treatment regimens with respect to quality of life [as measured  
218 by a disease specific (DQOL) questionnaire and general health (SF-36)  
219 questionnaire];

220 4. Compare the two treatment regimens with respect to all healthcare related costs:  
221 actual cost of the pharmacologic agents, glucose monitoring supplies, all other  
222 pharmacologic (non-study related) and non-pharmacologic healthcare related  
223 costs (outpatient and inpatient, diabetes related and non-diabetes related). We will  
224 also compare actual physician time spent during office visits and non-visit related  
225 care of these patients. While no actual dollar amount can be attached to this  
226 (phone visits and longer office visits required by the need for extra patient  
227 education are not customarily reimbursable) time commitment is of great  
228 relevance to our physicians who care for these very complex patients.  
229

230 **Primary outcome:**

231 Change in HbA1c from randomization to 26 weeks of therapy.  
232

233 **Secondary outcomes:**

- 234 1. The main secondary outcome is a less traditional but very patient-centric and  
235 clinically meaningful composite outcome of HbA1c <7% AND no documented  
236 hypoglycemia (capillary glucose level <56 mg/dl) AND no significant weight  
237 gain (<3% body weight) during the 6-mo study follow-up;
- 238 2. % reaching target HbA1c of <7% at end of study;
- 239 3. 7-point glucose profile results;
- 240 4. % patients reaching pre-specified “treatment failure” outcome;
- 241 5. Change in weight from baseline (both absolute weight lost and percent of body  
242 weight);
- 243 6. % patients with weight loss >5% of body weight;
- 244 7. Number of hypoglycemic episodes defined as mild (symptoms of hypoglycemia  
245 confirmed by a CBG reading of <70 mg/dl), moderate (any CBG reading <56  
246 mg/dl), severe (need for help to recover regardless of CBG reading);
- 247 8. Number of patients experiencing any hypoglycemic episodes;
- 248 9. DQOL questionnaire score;
- 249 10. SF-36 questionnaire score;

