 457 meals taken daily. Meal-time insulin titration, if needed, can be either patient driven (see  
 458 table below) or physician-directed during the scheduled follow-up visits (phone or in  
 459 person), as well as any unscheduled patient-initiated visits (if applicable).

460

461 Novolog patient self-titration table:

Glucose prior to lunch	Change in breakfast insulin dose	Glucose prior to dinner	Change in lunch insulin dose	Glucose prior to bedtime	Change in dinner insulin dose
<54	-2 units	<54	-2 units	<54	-2 units
55-69	-1 unit	55-69	-1 unit	55-69	-1 unit
70-120	No change	70-120	No change	70-130	No change
121-160	+1 unit	121-160	+1 unit	131-180	+1 unit

>160	+2 units	>160	+2 units	>180	+2 units
------	----------	------	----------	------	----------

462

463 **Rescue therapy:**

464 Should any patients randomized to liraglutide treatment experience persistent  
465 hyperglycemia (defined as a confirmed Hb1c>10%) at the 3-mo visit (visit 5), meal-time  
466 insulin aspart will be initiated per the same protocol as above. This is a pre-specified  
467 “treatment failure” end-point. Following initiation of rescue therapy patients will  
468 continue all scheduled visits and procedures through the end of the trial.

469

470 Should any patients randomized to the “standard of care” group experience persistent  
471 hyperglycemia (defined as a confirmed HbA1c >10%) at the 3-mo visit (visit 5),  
472 treatment and insulin titration will continue as scheduled. This is also a pre-specified  
473 “treatment failure” end-point.

474

475 A graphical review of the visit procedures and timing is presented below:

Visit	1	2	3	4	5	6
Time	3-7	0	2 weeks	1	3	6
Type	Office	Office	Phone	Office	Office	Office
Consent	x					
I&E criteria	x					
Randomization criteria		x				
Randomization		x				
Physical exam	x			x	x	x
Height	x					
Vitals (weight, BP, pulse)	x	x		x	x	x
Dietary counseling	x	x	x	x	x	x
Lifestyle counseling	x	x	x	x	x	x
7-point glucose		x				x
Labs (HbA1c, lipids, CMP, Hb)	x				x	x
Dispense trial drug		x		x	x	
Hypoglycemia assessment	X	X	X	x	x	x
Frequency of glucose monitoring				x	x	x
Titrate insulin		x	x	x	x	
Liraglutide titration (if applicable)			x			
Insulin dose assessment		x	x	x	x	x
Compliance assessment				x	x	x
# daily injections				x	x	x
QoL questionnaires (DQOL and SF36)		x				x
AE and SAE assessment		x	x	x	x	x
Pregnancy test (if needed)	x	x		x	x	x
Physician time assessment		x	x	x	x	x

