- 649 • Other adverse reactions associated with detemir insulin and/or aspart insulin  
650 include injection site reactions, lipohypertrophy, rash, itching.
- 651 • Needles and insulin pens should never be shared.

652

653 Risk of Metformin:

654

655 Very common (1-10 in 100 patients):

- 656 • Abdominal or stomach discomfort
- 657 • Decreased appetite
- 658 • Diarrhea
- 659 • Bloating
- 660 • Low serum Vitamin B12 levels without clinical manifestations

661

662 Precautions:

- 663 • Lactic Acidosis: Lactic acidosis is a very rare, but serious, metabolic complication  
664 that can occur due to Metformin accumulation during treatment with Metformin  
665 HCl; when it occurs, it is fatal in approximately 50% of cases. Lactic acidosis  
666 may also occur in association with a number of pathophysiologic conditions,  
667 including diabetes mellitus. Metformin should be discontinued immediately and  
668 health care provider should be promptly notified if unexplained increase in  
669 breathing rate, muscle aches, fatigue and unusual somnolence occur.
- 670 • Patients with Renal disease or renal dysfunction (e.g., as suggested by eGRF <30  
671 ml/min) should not use metformin
- 672 • Metformin should be temporarily discontinued 48h prior to radiologic studies  
673 involving intravascular administration of iodinated contrast materials 48h prior to  
674 procedure to avoid increased risk of development of lactic acidosis and restarted  
675 24h after the procedure.
- 676 • Excessive alcohol intake, either acute or chronic should be avoided while  
677 receiving Metformin.

678

679 **SAFEGUARDS AND PRECAUTIONS TO MINIMIZE RISKS/HARMS:**

- 680 • Hypoglycaemia episodes will very closely monitored through the study using self-  
681 glucose monitoring. Review of blood glucose diary and hypoglycaemic events  
682 will be discussed during office, phone visits and as needed. Patient will be  
683 instructed during randomization visit on how to properly handle mild, moderate and  
684 severe hypoglycemic episodes and how to reduce their basal insulin doses  
685 according to study protocol. Those instructions will be reinforced as needed  
686 during the study.
- 687
- 688 • Should any patients randomized to liraglutide treatment experience persistent  
689 hyperglycemia (defined as Hb1c>10%) at the 3-mo visit (visit 5), meal-time  
690 insulin aspart will be initiated per the same protocol as the standard group
- 691

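### Treatment failure is a yes/no status set at the month-3 visit and listed as a percentage, but the SAP assigns it a logrank test instead of its own logistic rule for binary endpoints

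*Combined protocol and SAP*

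**What the plan says.** - **Outcome.** Secondary outcome 4 is the percentage of "patients reaching pre-specified" treatment failure. It is listed as a proportion, not as a time.
- **Definition.** Under Rescue therapy, failure in the liraglutide arm is "hyperglycemia (defined as a confirmed Hb1c>10%) at the 3-mo visit (visit 5), meal-time" insulin then being started. In the basal-bolus arm it is "hyperglycemia (defined as a confirmed HbA1c >10%) at the 3-mo visit (visit 5"), with treatment continuing as scheduled. After baseline, HbA1c is scheduled only at months 3 and 6 (Assessments for Efficacy), and the month-6 value is not part of the definition.
- **Restated definition.** The section on safeguards and precautions repeats the rule without requiring confirmation: "hyperglycemia (defined as Hb1c>10%) at the 3-mo visit (visit 5), meal-time" insulin for the liraglutide arm, and likewise for the other arm.
- **Analysis.** The Statistical Analysis Plan states for binary outcomes that "secondary endpoints will also be assessed with logistic regression models. Group" comparisons of continuous outcomes use a mixed model. It then names the logrank test for treatment failure: "outcome variables will be analysed with mixed model repeated analysis. The logrank test" "will be used to compare the pre-specified “treatment failure” end-point between groups".
- **Not stated.** The documents give no event date (scheduled visit, actual visit or confirmation), no visit-5 window, no censoring rule, and no rule for patients without a visit-5 HbA1c.

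**The concern.** A logrank test compares event times. Here the event can be reached at only one scheduled visit, so there is no time information to compare. Any difference in recorded times reflects scheduling and attendance.

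Three things are at stake:

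1. The test yields a p-value but no estimate of the percentage that the outcome list promises.
2. Its behaviour depends on how event and censoring dates are coded, which the plan leaves open.
3. Under default logrank coding, a patient who leaves before visit 5 is censored and is absent from the only risk set that counts. The comparison then covers only patients who reach visit 5. The Withdrawal Criteria allow removal for unchanged or worse diabetes control, so such absences may be related to the endpoint.

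**Working it through.** **The plan's own figures.** The documents give no failure rate, event count or power for this outcome. The only nearby figure is the primary sizing. With margin 0.4, SD 0.5, one-sided alpha 0.025 and 44 per group, the noncentral t gives power 0.960, as stated. The randomised total is 88/(1 − 0.12) = 100, also as stated. Neither depends on the point made here.

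**Step 1: all failures at one nominal time.** With a single event time, the logrank statistic is the Pearson 2x2 chi-square times (N − 1)/N, where N counts patients who reach visit 5. Assumed counts of 10/50 vs 4/50 give:

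- Pearson = 100 × (10×46 − 40×4)² / (50×50×14×86) = 2.990, p = 0.084.
- Logrank = 2.990 × 99/100 = 2.960, p = 0.085.

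The logrank adds nothing here, and does no harm.

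**Step 2: actual visit dates.** Assumed inputs are 47 per arm (midway between 44 completers and 50 randomised), visit-5 dates with SD 5 days, and two-sided alpha 0.05. The null scenarios have 15% failure in both arms. The power scenario is 25% vs 8% with no shift. Values come from simulation with about 4,000 trials per scenario and vary by 0.01 to 0.02 between runs.

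| Coding of non-failures | Type I error, no shift | 3-day shift | 5-day shift | Logrank power | 2x2 power |
|---|---|---|---|---|---|
| Censored at own visit-5 date | 0.05 | 0.17 | 0.37 | 0.54 | 0.64 |
| At risk to month 6 | 0.05 | 0.05 | 0.05 | 0.63 | 0.64 |

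In the first row every patient leaves the risk set on the visit-5 date, as an event or as censored. The arm seen later has more follow-up for the same number of failures and so appears to have a lower failure rate. The 2x2 test stays close to 0.05 under the null throughout.

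A wider check used 50 per arm, SD 7 days, and shifts of 7 and 14 days:

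- Non-failures censored at visit 5, 7-day shift: type I error 0.28 to 0.78 as the common failure rate goes from 10% to 40%.
- Non-failures at risk to month 6, 14-day shift: about 0.055 at 10% to 20% failure, and 0.11 at 40%.

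**Step 3: patients who leave before visit 5.** Assume 50 per arm, six observed failures in each arm, and 12 early withdrawals in total, which is the planned 12% of 100.

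- Split 10 vs 2, withdrawals censored: 6/40 = 15.0% vs 6/48 = 12.5%, logrank p = 0.74.
- Same split, all withdrawals counted as failures: 16/50 = 32% vs 8/50 = 16%, Pearson p = 0.061.
- Split 6 vs 6: p = 1.00 either way.

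The handling rule matters only if early withdrawal is unbalanced between arms. This is a missing-status problem: a 2x2 test confined to visit-5 attenders would have it too.

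**The case against.** The strongest reply is that no harm is shown. The plan does not say that actual dates will be used or that non-failures will be censored at visit 5. Rescued patients continue all visits to the end of the trial, and basal-bolus failures continue as scheduled. Follow-up to month 6 is therefore the more natural reading, and under it the inflation vanishes and the power loss is about 0.01 to 0.02. Both arms share one visit schedule, and nothing in the documents suggests that one arm attends later. With no shift, type I error is nominal under either coding. This is also one of 25 secondary outcomes.

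All of that stands. A reader might infer that visit timing does drive the result, or that the plan censors early withdrawals. Neither is written: the first needs a particular coding together with a shift between arms, and the second is only the test's default.

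A reader might also infer that poor-control withdrawals must count as failures in the main analysis. The documents do not support that. No HbA1c is scheduled between screening and visit 5, and the treating study doctor is unblinded, so this would add an open-label judgement to a laboratory endpoint. Nor can a large change in p-value from such recoding be charged to the logrank test. On assumed counts of 8/44 vs 3/50, Pearson also gives p = 0.067. Recoding six withdrawals in one arm and none in the other, to 14/50 vs 3/50, gives p = 0.003 through the recoding alone.

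What the reply does not remove is the mismatch between the test, the outcome as listed, and the SAP's own rule for binary endpoints.

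**Conclusion.** The mismatch holds on the text alone and needs no simulation: a binary status, listed as a percentage and reachable at one scheduled visit, is given a time-to-event test. At best that test equals the 2x2 comparison among visit-5 attenders; in no case does it estimate the percentage.

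The size of any harm is conditional. It ranges from none (nominal times) or negligible (non-failures at risk to month 6, failure uncommon) to type I error of about 0.17 to 0.37, for shifts of 3 to 5 days with non-failures censored at visit 5. Under that censoring with no shift, the cost is power of about 0.54 instead of 0.64. All failure rates, date spreads, shifts and withdrawal splits are assumptions.

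The change should be made because it is nearly free, but it concerns one secondary outcome and leaves the primary analysis and sample size untouched.

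**What to change.** 1. Replace the logrank sentence in the Statistical Analysis Plan. Report the proportion failing at month 3 in the ITT set, compare arms by logistic regression with the two stratification factors (insulin treatment at screening; BMI cutoff 37 kg/m²), and give a risk difference with 95% CI.
2. State how patients without a visit-5 HbA1c are handled.
3. Add a sensitivity analysis, and only that, in which withdrawal for poor control before visit 5 counts as failure.
4. Reconcile Rescue therapy with the safeguards section on whether the HbA1c must be confirmed, so that the endpoint has one definition.

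The cost is a few sentences. No data collection, visit or sample-size change is needed. Keeping the poor-control rule out of the main analysis leaves the laboratory definition of the endpoint intact.
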